- ALKS 3831: (ie, olanzapine [dose determined by the PI] plus samidorphan [10 mg])
- Olanzapine (dose determined by the PI) plus placebo

Subjects randomized to double-blind treatment will be followed for a minimum of 9 months and a maximum of 15 months. Visits during the double-blind period will be every 2 weeks. Each visit will consist of clinical assessments plus drug dispensing or drug dispensing only. After the end of the double-blind treatment period, subjects will complete a 3-week safety follow-up period.

Abbreviation: V = Study Visit; ALKS 3831=olanzapine + samidorphan

Number of Subjects Planned:

Approximately 450 subjects will enter the open-label olanzapine period at Visit 2. Of those, approximately 270 are expected to be randomized at Visit 8.

Main Criteria for Inclusion:

Men and women 18 through 65 years of age (inclusive) with a DSM-IV-TR diagnosis of schizophrenia and a DSM-5 diagnosis of AUD who meet pre-specified symptom severity criteria may be eligible for this study. At a minimum, subjects must also meet sponsor criteria for a recent (within 6 months) exacerbation of schizophrenia symptoms and have experienced at least 10 drinking days in the 30 days prior to screening (as measured by the Timeline Follow-Back [TLFB] method), with at least 2 of these drinking days meeting criteria for a heavy drinking day (4 drinks in a day for women and 5 drinks in a day for men), to be eligible for this study.

Investigational Product Dosage, Duration, and Mode of Administration:

ALKS 3831 refers to the combination of olanzapine and samidorphan. In this study, olanzapine and samidorphan will be coadministered orally using separate tablets for olanzapine and samidorphan to be taken once daily. Commercially available olanzapine for oral administration will be dispensed by the investigative site. All subjects will take olanzapine for the entire duration of the study.

Alkermes will provide samidorphan as 10 mg tablets. All subjects will take open-label ALKS 3831 for 2 weeks prior to randomization. Subjects randomized to the double-blind treatment period will take ALKS 3831 (olanzapine plus samidorphan) or olanzapine plus placebo for the duration of the double-blind period.

Whether or not samidorphan is classified as a controlled substance varies from country to country; some

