6.1. Analysis Visit Windows

Scheduled analysis visits are visits upon scheduled time points as specified in the protocol ([Table 1-3 Schedule of Visits and Assessments](#)).

Scheduled analysis visits during the study period will be the same as the nominal visits collected in eCRF. There will be one valid value of assessment kept for each scheduled analysis visit in summary/analysis statistics.

Unscheduled visits are visits with data not collected on the scheduled time point. Unscheduled visits will not be used for by-visit summary/analysis statistics unless specified otherwise.

All unscheduled visits will be included as collected in eCRF in listings.

The V38/ET visit can be mapped to a scheduled visit and be used for analysis and summaries only if there is no valid value already at the mapped visit.

A mapped V38/ET visit will be treated as a scheduled visit to be included in table summaries. Otherwise, it will be treated as an unscheduled visit.

Four rules will be used to map an ET visit.

- First, a 7-day (inclusive) window (\leq last dose date + 7) will be used to determine if the assessment at the ET visit is considered to be an on-treatment result. If an ET visit is within 7 days after the last dose of samidorphan/placebo, it will be considered as a valid on-treatment visit.
- Second, visit windows (inpatient stay is excluded) will be applied to determine to which visit a V38/ET valid on-treatment assessment can be mapped to. Visit windows are defined in Table 8 below.

Table 8: Visit Window Definition

Analysis Visit to be Mapped to	Target Study Day	Visit Day	Visit Window
Visit 2	Study day -28	Day -28	[-28, -25]
Visit 3	Study day -21	Day -21	[-24, -18]

Table 8: Visit Window Definition (Continued)

Analysis Visit to be Mapped to	Target Study Day	Visit Day	Visit Window
Visit 4	Study day -14	Day -14	[-17,-11]
Visit 5	Study day -7	Day -7	[-10, 0]
Visit 6	Study day 1	Day 1	1
Visit 7	Study day 8	Day 8	[2, 11]
Visit 8	Week 3	Day 15	[12, 21]
Visit 9	Week 5	Day 29	[22, 35]
Visit 10	Week 7	Day 43	[36, 57]
Visit 12	Week 11	Day 71	[58, 85]
Visit 14	Week 15	Day 99	[86, 113]
Visit 16	Week 19	Day 127	[114, 141]
Visit 18	Week 23	Day 155	[142, 169]
Visit 20	Week 27	Day 183	[170, 197]
Visit 22	Week 31	Day 211	[198, 225]
Visit 24	Week 35	Day 239	[226, 253]
Visit 26	Week 39	Day 267	[254, 281]
Visit 28	Week 43	Day 295	[282, 309]
Visit 30	Week 47	Day 323	[310, 337]
Visit 32	Week 51	Day 351	[338, 365]
Visit 34	Week 54	Day 379	[366, 393]

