Visit 36	Week 59	Day 407	[394, 421]
Visit 38	Week 63	Day 435	[422, Day of Safety follow-up -1]

Visit Day is calculated as visit date – date of the first dose of ALKS 3831 (scheduled on Visit 6) + 1.

- Third, V38/ET visit can only be mapped to the same treatment period as the last scheduled visit. Otherwise, ET visit will be considered as unscheduled visit. Additionally, V38/ET visit can only be mapped to a scheduled visit that a particular assessment is taken based on the protocol.
- Four, for subjects who discontinued before visit 6, an on-treatment V38/ET results as defined above, will be mapped to the next scheduled visit, if within the same treatment period as the last scheduled visit.

Last post baseline values are defined as the last valid post baseline values collected for each subject during the treatment period or a specified reporting period.

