7. GENERAL STATISTICAL METHODOLOGY

In general, summary statistics (n, mean, standard deviation [SD], median, minimum, and maximum for continuous variables, and number and percentage of subjects in each category for categorical variables) will be provided by treatment group. All summary tables will be based on observed data, and missing values will not be imputed unless otherwise indicated. Measurements collected from unscheduled visits or repeated assessments will not be included in the by-visit summary tables or figures, or the derivation of the last post-baseline value during treatment, but will be included in the analyses for the PCS post-baseline values, and subject listings. Source data for the summary tables and statistical analyses will be presented as subject data listings.

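### SAP 6.1 defines an on-treatment early-termination visit by the last samidorphan/placebo dose, so read literally its rule for subjects who leave before Visit 6 applies to nobody

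*SAP*

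**What the plan says.** SAP 6.1 gives four rules for placing a V38/ET visit in the by-visit analyses.

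- **Rule 1** sets a window of 7 days after the last dose date. That window "will be used to determine if the assessment at the ET visit is considered to be an on-treatment result"; this sentence names no drug. The next sentence does: "If an ET visit is within 7 days after the last dose of samidorphan/placebo, it will be considered as a valid on-treatment visit".
- **Rule 2** uses the Table 8 windows, whose note says "Visit Day is calculated as visit date – date of the first dose of ALKS 3831".
- **Rule 3** allows mapping only within the treatment period of the last scheduled visit, and only to a visit at which the protocol schedules that assessment.
- **Rule 4** is the special case: "Four, for subjects who discontinued before visit 6, an on-treatment V38/ET results as defined above, will be mapped to the next scheduled visit", but only "if within the same treatment period as the last scheduled visit".

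An ET visit that is not mapped counts as unscheduled. SAP 7 states the consequence: "Measurements collected from unscheduled visits or repeated assessments will not be included in the by-visit summary tables or figures". The same section also keeps such values out of the last post-baseline value, but retains them for listings and for analyses of potentially clinically significant (PCS) values.

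Samidorphan is first given at Visit 6 (SAP 1.2; Protocol 8). Protocol 9.1 counts olanzapine as a study drug.

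**The concern.** Rule 4 exists for one group: subjects who stop during the open-label olanzapine period. They have taken olanzapine only. If on-treatment depends on a samidorphan/placebo dose, none of them can meet the condition, and the rule defeats its own purpose.

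At stake are descriptive summaries of the open-label olanzapine period. Protocol 7.4 asks subjects who withdraw to attend an ET visit that matches Visit 38, so weight, vital signs, movement scales, laboratory tests, ECG and PANSS are collected when they stop. If those values are treated as unscheduled, the by-visit summaries describe subjects at the visits they attended and leave out the measurements taken at exit. The retention of unscheduled values for PCS analyses helps little here, because SAP 3.8.3 to 3.8.5 specify the PCS tables for laboratory tests, weight, vital signs and ECG for the double-blind period only. Two programmers could also follow SAP 6.1 in good faith and produce different open-label tables.

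**Working it through.** The plan states no figure to reproduce. The check applies the rules to the visit schedule.

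**Inputs**

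- Open-label olanzapine period: Visits 2 to 5. Visit 6 opens the ALKS 3831 period (Protocol Table 1).
- Assessment slots from Visit 2 on (Protocol Table 1): weight with waist, vital signs and C-SSRS at every visit; VAS at Visits 3, 5 and 7; AIMS/SAS/BARS at Visits 2, 4 and 6; PANSS, CGI-S, TLFB, laboratory tests and ECG at Visits 2 and 6.
- Subject: last scheduled visit 2, 3, 4 or 5, olanzapine only, ET 3 days after the last olanzapine dose (assumed; any lag up to 7 days gives the same result).
- Combinations: 10 assessment types × 4 last visits = 40.

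**Reading A: last dose means samidorphan/placebo.** No such dose exists, so rule 1 fails every time: 0 of 40 combinations map. Rule 2 gives no other route, because Visit Day is counted from an ALKS 3831 dose these subjects never took.

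**Reading B: last dose means any study drug, including olanzapine.** Rule 1 is met; the same-period and scheduled-assessment conditions then decide.

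| Assessment | Maps to the very next visit | Maps to the next visit with that assessment |
|---|---|---|
| Weight/waist | 3 (V2→3, V3→4, V4→5) | 3 |
| Vital signs | 3 (same) | 3 |
| C-SSRS | 3 (same) | 3 |
| VAS | 2 (V2→3, V4→5) | 3 (adds V3→5) |
| AIMS/SAS/BARS | 1 (V3→4) | 2 (adds V2→4) |
| PANSS, CGI-S, TLFB, laboratory tests, ECG | 0 | 0 |
| **Total of 40** | **12** | **14** |

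The remaining 40 − 12 = 28 or 40 − 14 = 26 combinations fail under either reading. For the five assessments in the last row, the next slot is Visit 6, in another period. For a subject whose last visit was Visit 5, nothing maps, for the same reason.

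**What changes in the tables.** C-SSRS is summarized by period (SAP 3.8.7), so visit mapping does not matter for it. VAS is an efficacy measure, and SAP 3.1 summarizes efficacy for the double-blind period unless stated otherwise, so it matters only if an open-label VAS summary is produced. That leaves weight/waist, vital signs and movement scales: 12 − 3 − 2 = 7, or 14 − 3 − 3 = 8, combinations.

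**How many subjects.** The protocol synopsis says "Approximately 450 subjects will enter the open-label olanzapine period at Visit 2" and expects about 270 to be randomized: 450 − 270 = 180, and 180 / 450 = 40%. No split between leaving before and after Visit 6 is given, so the number leaving before Visit 6 lies between 0 and about 180.

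**The case against.** The strongest reply is that this is loose wording and not a dead rule. Rule 1's first sentence gives the window with an unqualified last dose date; rule 4 picks up that sentence's term, on-treatment result; the second sentence gives a sufficient condition and does not say only if; and olanzapine is a study drug. Since rule 4 is expressly for subjects who leave before Visit 6, the reading that makes it work is the natural one. Rule 4 also goes straight to the next scheduled visit, so the missing Visit Day does no harm. The dataset and programming specifications, which SAP 6 and 8 place in separate documents, may already settle the matter.

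Most of this stands. A reader might infer that rule 4 can never apply; the documents do not support that, because a workable reading exists. A reader might also infer that the on-treatment definition is what removes PANSS, laboratory and ECG values; it is not, since the period and schedule conditions block them under any definition. What remains is that the only sentence naming a drug names one these subjects never took, and rule 4 points back to that definition. The SAP text should settle this itself.

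**Conclusion.** The point holds as a conflict between two sentences of rule 1 for subjects who leave before Visit 6. Read literally, rule 4 applies to nobody, and ET weight, waist, vital signs and, where a same-period slot exists, movement scale and VAS values drop out of the open-label olanzapine by-visit and last post-baseline summaries. Read with olanzapine as the last dose, they are used.

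The size cannot be stated from the documents. The ceiling is about 180 of 450 (40%), and the true figure is smaller to the extent that subjects leave after Visit 6 or do not attend ET within 7 days. The 180 includes subjects who reach Visit 6 and then fail the randomization criteria in Protocol 7.3, and Protocol 7.4 foresees refusal and loss to follow-up. A reader might assume that half to three quarters of the 180 leave before Visit 6 (0.50 × 180 = 90 to 0.75 × 180 = 135) and count all of them as lost; neither the split nor full ET attendance has a source. Nor can one average leavers and stayers to size a bias in mean weight: a working rule 4 would place each ET weight at Visit 3, 4 or 5 according to when the subject left, not in one pooled mean.

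The consequence is minor. The affected summaries are uncontrolled and descriptive. AE, SAE, disposition and by-period C-SSRS summaries, the primary analysis and every randomized comparison are untouched.

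**What to change.** In SAP 6.1 rule 1, replace the drug-specific condition with: *within 7 days after the last dose of the study drug of the period in which the subject discontinued (olanzapine for the open-label olanzapine period; samidorphan/placebo thereafter)*. The wording should be period-specific. Simply saying any study drug would loosen the double-blind window, because Protocol 9.1 continues olanzapine to the end of the study. It would also help to say whether the next scheduled visit in rule 4 means the very next visit or the next one with that assessment. The cost is one or two clauses and matching changes to the dataset specification; no new data are needed.

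Separately and optionally, ET values of PANSS, CGI-S, TLFB, laboratory tests and ECG, and all ET values after Visit 5, could be used through an added end of open-label olanzapine row (Visit 6 or on-treatment ET). The plan does not promise such a row, and it would mix different times on olanzapine. If it is not wanted, one sentence saying that these ET values are listed only would be enough.

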6.2. Handling of Partial Dates of Concomitant Medication

Partial start dates of prior and concomitant medications will be assumed to be the earliest possible date consistent with the partial date. Partial stop dates of prior and concomitant medications will be assumed to be the latest possible date consistent with the partial date. In the case of completely missing stop date, medication will be assumed to be ongoing.

6.3. Handling of Safety Data

All efforts should be made to obtain the missing information from the investigator. For C-SSRS, vital signs, laboratory testing (chemistry, hematology, urinalysis), and 12-lead ECGs, only observed data will be used for analyses, and missing data will not be imputed.

7. GENERAL STATISTICAL METHODOLOGY

In general, summary statistics (n, mean, standard deviation [SD], median, minimum, and maximum for continuous variables, and number and percentage of subjects in each category for categorical variables) will be provided by treatment group. All summary tables will be based on observed data, and missing values will not be imputed unless otherwise indicated. Measurements collected from unscheduled visits or repeated assessments will not be included in the by-visit summary tables or figures, or the derivation of the last post-baseline value during treatment, but will be included in the analyses for the PCS post-baseline values, and subject listings. Source data for the summary tables and statistical analyses will be presented as subject data listings.

7.1. Reporting Precision

Summary statistics will be presented to the following degree of precision, unless otherwise specified:

Table 9: Degree of Precision

Statistics	Degree of Precision
Mean, Median, Confidence limit boundaries	One more than the raw data, up to 3 decimal places.
Standard deviation, Standard error	One more than the mean, up to 3 decimal places
Minimum, Maximum	The same as the raw data, up to 2 decimal places
p-value	Rounded to 3 decimal places and therefore presented as 0.xxx; p-values smaller than 0.001 as '<0.001'; p-values greater than 0.999 as '>0.999'.
Percentage	One decimal place. A percentage of 100% will be reported as 100%. Percentages of zero will be reported as 0.

Fractional numeric values will be presented with a zero to the left of the decimal point (for example, 0.12 – 0.30).

For weight, height, and body mass index (BMI), one decimal place will be used for summary statistics.

8. PROGRAMMING SPECIFICATIONS

Programming specifications will be provided in a separate document.

9. MOCK TABLE LISTING AND FIGURES (TLF)

Mock-up tables and listings will be provided in a separate document.

